## **STUDY POPULATION**

### **Inclusion Criteria:**

- 1) Signed written informed consent
  - Before any study procedures are performed, subjects will have the details of the study described to them, and they will be given a written informed consent document to read. Then, if subjects consent to participate in the study, they will indicate that consent by signing and dating the informed consent document in the presence of study personnel.
- 2) Target Population
  - Subjects with a diagnosis of Type 2 diabetes mellitus using criteria of the American Diabetes Association.
  - Currently treated with any combination of the following anti-diabetic therapies: metformin (1-2 grams), insulin, GLP-1 agonists, a DPP-IV inhibitor, or sulfonylureas
  - HbA1C between 7.0% and 10% (both inclusive)
  - BMI 25-39.9 kg/m^2 both inclusive.

One of the prime outcome measure is estimation of renal function and accurate eGFR staging: Estimated Glomerular Filtration Rate Serum Cr should be used to estimate glomerular filtration rate (GFR). Estimated GFR (eGFR) is commonly reported by laboratories or can be estimated using formulae such as the Modification of Diet in Renal Disease (MDRD) study equation or the Chronic Kidney Disease Epidemiology Collaboration (CKD-EPI) equation. The latter is the preferred GFR estimating equation. GFR calculators are available at [http:// www.nkdep.nih.gov](http://www.nkdep.nih.gov).

Abnormal urinary albumin excretion and eGFR may be used to stage chronic kidney disease (CKD). The National Kidney Foundation classification (Table below) is based on **both kidney damage (UACR at or above 30 mg/g Cr) and eGFR**.

Normal UACR is defined as less than 30 mg/g Cr, and increased urinary albumin excretion is defined as at or above 30 mg/g Cr. Because of variability in urinary albumin excretion, ideally two (at least one) specimens of UACR should have been collected within a 3- to 6-month period before considering a patient to have albuminuria.

Stage -- Description -- GFR (mL/min/1.73 m^2 )

Stage 1 Kidney damage\* with normal or increased GFR  $\geq 90$

2 Kidney damage\* with mildly decreased eGFR 60–89

3A Moderately decreased eGFR 45–59

3B Moderately decreased eGFR 30–45

4 Severely decreased eGFR 15–29

5 Kidney failure, 15 or dialysis

\*Kidney damage is defined as abnormalities on pathological, urine, blood, or imaging tests.

### 3) Age and Reproductive Status

- Men and women, 30 to 70 years of age.
- Enrolled women must not be pregnant, should not be breast-feeding and should not be taking estrogen hormone replacement therapy (HRT) during the study.

#### ***The following is a definition of Women of Child Bearing Potential (WOCBP):***

- Women using the following methods to prevent pregnancy: Oral contraceptives, other hormonal contraceptives (vaginal products, skin patches, or implanted or injectable products), or mechanical products such as intrauterine devices or barrier methods (diaphragm, condoms, spermicides).
- Women who are practicing abstinence.
- Women who have a partner who is sterile (e.g., due to vasectomy). WOCBP must be using an acceptable method of contraception to avoid pregnancy throughout the study and for up to 4 weeks after the last dose of study drug in such a manner that the risk of pregnancy is minimized.
- WOCBP must have a negative serum or urine pregnancy test result within 0 to 72 hours before the first dose of study drug.
- Women must not be breast-feeding.

#### ***Post-menopause is defined as:***

- Women who have had amenorrhea for  $\geq 12$  consecutive months and/or who have a documented serum follicle-stimulating hormone (FSH) level  $> 35$  mIU/mL.
- Women who have irregular menstrual periods and a documented serum FSH level  $> 35$  mIU/mL.
- Women who are taking hormone replacement therapy (HRT).

#### **Exclusion Criteria:**

- Type 1 diabetes mellitus
- History of hyperosmolar non-ketotic coma
- Abnormal CBC that is judged by physician to be unsafe to enroll or low hematocrit ( $< 28$  UNITS).
- History of pancreatitis
- History of diabetic ketoacidosis in the last 3 months
- History of cancer (except basal cell carcinoma and cancer that is cured or not active or being treated in the past 5 years)
- Heart attack or stroke within 6 months of screening

- Clinically significant coronary and/or peripheral vascular disease that would be unsafe to enroll in the study. \*
- Statin use started or dose change in the last 3 months. \*
- CKD Stages 3B,4 and 5 (see definition above)
- Use of oral or injectable anti-diabetic medication other than any combination of the following anti-diabetic therapies: metformin (1-2 grams), insulin, GLP-1 agonists, a DPP-IV inhibitor, or sulfonylureas currently, or in the past 1 month. \*
- Use of consistent long-term steroid medication (oral, inhaled, injected) within the last 3 months. \*
- Uncontrolled inflammatory disease, or current chronic use of anti-inflammatory drugs within the last 3 months. \*
- Implanted devices (e.g., pacemakers) that may interact with Body Composition scale
- Untreated Systolic Blood Pressure > 150 mmHg and diastolic Blood Pressure > 90 mmHg
- Active wounds or recent surgery within 3 months. \*
- Untreated hyper/hypothyroidism

*\*These criteria may be allowed, judged on a case by case basis by the PI, with appropriate rationale.*

#### **Physical and Laboratory Test Findings**

- Pre-existing liver disease and/or ALT and AST >2.5X's UNL
- Serum creatinine levels  $\geq 2.0$
- Estimated CrCl < 45 mL/min (measured by eGFR value)
- Triglycerides >450 mg/dL

#### **Allergies and Adverse Drug Reactions**

- Subjects with a history of any serious hypersensitivity reaction to Cana or another SGLT2 inhibitor.

#### **Sex and Reproductive Status**

- Women in reproductive age group will be included in the study but encouraged to use contraceptive method to avoid pregnancy within 16 weeks of study duration.
- Women who are pregnant or breast-feeding will be excluded.

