#### **Other Exclusion Criteria**

- Prisoners or subjects who are involuntarily incarcerated.
- Subjects who are compulsorily detained for treatment of either a psychiatric or physical (e.g., infectious disease) illness.
- Patients who are active smokers
- Patients who are pregnant
- Nursing women
- Post-menopausal women who are on estrogen hormone replacement therapy will be excluded.
- Patients on low dose oral contraceptives will be allowed to participate as these formulations contain very low amounts of estrogens.

- Eligibility criteria for this study have been carefully considered to ensure the safety of the study subjects and to ensure that the results of the study can be used. It is imperative that subjects fully meet all eligibility criteria.

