### **IV. Pregnancy**

All initial reports of pregnancy must be reported to Janssen Scientific Affairs by the Sponsor Investigator **within 24 hours of their awareness of the event** using the Serious Adverse Event Form. Abnormal pregnancy outcomes (e.g. spontaneous abortion, stillbirth, and congenital anomaly) are considered serious adverse events and must be reported using the Serious Adverse Event Form.

Any subject who becomes pregnant during the study must be promptly withdrawn from the study and discontinue further study treatment.

Because the effect of the Janssen medicinal product on sperm is unknown, pregnancies in partners of male subjects exposed to a Janssen medicinal product will be reported by the Sponsor Investigator **within 24 hours of their awareness of the event** using the Serious Adverse Event Form. Depending on local legislation this may require prior consent of the partner.

Follow-up information regarding the outcome of the pregnancy and any postnatal sequelae in the infant will be required.

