**Week -2:** Subjects will be phone screened to determine initial eligibility. If the phone-screening indicates possible eligibility, then the subjects will come to an in-person screening visit that same week (If within two weeks that is acceptable).

In-person screening (Week -2): Subjects will be screened and eligibility will be verified based on physical and laboratory tests. Equal numbers of male and female patients will be recruited.

**Week 0:** At this stage patients will be randomized into the study. Subjects will have the first set of measurements. We will make sure that patients still meet the inclusion criteria. They will be started on medication or placebo.

**Weeks 0, 8 and 16:** Subjects will all have the same measurements and will continue on study medication or placebo. All primary and secondary measures as outlined before will be carried out.

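### Sex and Reproductive Status only encourages contraception, contradicting the inclusion rule that women of childbearing potential must use it

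*Combined protocol and SAP*

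**What the plan says.** Both statements are current text in section 3.

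- **Inclusion side**, item 3 (Age and Reproductive Status), in the list headed as a definition of WOCBP: "WOCBP must be using an acceptable method of contraception to avoid pregnancy throughout the study and for up to 4 weeks after the last dose".
- **Exclusion side**, Sex and Reproductive Status: women in the reproductive age group "will be included in the study but encouraged to use contraceptive method to avoid pregnancy within 16 weeks of study duration".

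Two other texts bear on how to read them. Other Exclusion Criteria closes with "It is imperative that subjects fully meet all eligibility criteria". The footnote to the Exclusion Criteria gives the investigator discretion ("These criteria may be allowed, judged on a case by case basis by the PI"), but only for items marked with an asterisk, and neither contraception sentence is marked.

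The remaining pregnancy provisions are:

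- pregnant women are excluded at entry;
- WOCBP need a negative test in the 72 hours before the first dose (same WOCBP list);
- urine tests are scheduled as needed at screening and at weeks 0, 8 and 16 (section 6);
- under section 5, IV. Pregnancy, "Any subject who becomes pregnant during the study must be promptly withdrawn from the study".

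The synopsis has no rule on contraceptive use and refers to the detailed criteria.

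**The concern.** One participant-safety rule appears as an obligation in one place and as advice in another. The two also seem to end at different times. The advisory sentence stands alone under a heading that names its subject. The mandatory one is run into the bullet about a sterile partner, inside a list presented as a definition. The weaker rule is thus the easier one to find.

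At stake is exposure of a pregnancy to study drug. Contraception is the only measure in the plan that acts before conception. The point concerns safety and eligibility; it has no bearing on the analysis.

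**Working it through.** The plan gives no figure to reproduce. The check sets the two statements side by side and then works out their reach.

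| | WOCBP list (inclusion item 3) | Sex and Reproductive Status |
|---|---|---|
| Force | must | encouraged |
| During treatment | whole study | the 16 weeks |
| After last dose | up to 4 weeks | nothing stated |

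**1. Where they collide.** A woman who uses contraception satisfies both. A woman who declines is ineligible under the first, while the second says that women like her will be included and encouraged.

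**2. Which governs.** No sentence ranks the two explicitly. The criteria are cumulative, however: Other Exclusion Criteria requires all of them to be met. The mandatory sentence is an inclusion requirement without an asterisk, so the investigator's case-by-case allowance does not reach it. A woman who declines therefore fails eligibility whatever the other sentence encourages.

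**3. Duration.** Take the study as the 16 weeks of treatment, as Study Design Overview does.

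- Advisory rule: 16 weeks, so 0 days after the last dose.
- Mandatory rule: at most 16 + 4 = 20 weeks. The post-dose part is 0 to 4 × 7 = 28 days, because *up to* sets a ceiling and no minimum.
- Difference: 0 to 28 days.

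**4. Whether another safeguard fills the gap.**

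- Exclusion at entry and the test in the 72 hours before dosing show that a woman is not pregnant at the start. They cannot prevent a later conception.
- The as-needed tests at weeks 0, 8 and 16 are 8 weeks apart, and none is scheduled after week 16, when only the week-20 telephone call remains.
- Withdrawal and 24-hour reporting follow a pregnancy that has already occurred.

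**5. How many women the rule covers.** The in-person screening text says "Equal numbers of male and female patients will be recruited", so 40 × 1/2 = 20 women is the planned ceiling. Ages run from 30 to 70, and the share of childbearing potential is not given. As an assumption, shares of 10%, 25% and 50% give 20 × 0.10 = 2, 20 × 0.25 = 5 and 20 × 0.50 = 10 women. How many of them would decline contraception is unknown.

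**The case against.** The strongest reply is that the answer can be derived from the documents. A reader might infer from the two sentences that the question is left open, or that the investigator may choose between them. The documents do not support that: all criteria must be met, the mandatory one is among them, and no waiver applies to it. The softer sentence can also be read as saying only that reproductive age is not in itself an exclusion. This part of the objection stands. The defect is one wrong sentence, and the plan is not without a governing rule.

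The safeguards are also stronger than the as-needed tests alone suggest. The pre-dose test is mandatory for WOCBP, adverse events are followed for 30 days after the last dose, and there is a week-20 call. That is correct, but none of these prevents conception during treatment.

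The duration difference may be zero, given the words *up to*. That also stands, so the contradiction in force carries the point and the duration is secondary.

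Finally, the consent pages were not available for this review and may state the rule correctly. No mismatch with them is claimed. Correct consent wording would reduce the practical risk but would not repair the eligibility text that staff apply.

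**Conclusion.** Wrong as written (patient safety). Sex and Reproductive Status contradicts the inclusion requirement. The inclusion requirement is the better-supported rule, so the advisory sentence is the one to correct.

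The contradiction is between an obligation and advice, with a post-dose difference of 0 to 28 days and a ceiling of 20 women in 40 subjects. The figures of 2, 5 or 10 women rest on assumed shares and show scale only. That staff might follow the weaker sentence is a plausible risk; the documents do not show that it happened.

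A reader might go on to infer that the post-dose weeks carry a known hazard. The documents give no washout or reproductive-toxicity information for women, so no harm rate is claimed, and they do not establish that exactly 4 weeks are needed. The case for a fixed period is that it can be applied uniformly. No power, sample-size or analysis figure is affected.

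**What to change.** 1. In Sex and Reproductive Status, replace the advisory sentence with the mandatory rule, for example: women of childbearing potential must use an acceptable contraceptive method for the whole study and for 4 weeks after the final dose.
2. In the WOCBP list, delete *up to*, so that both places give the same fixed 4 weeks. This firms up the inclusion rule as well as aligning the other sentence with it.
3. Check that the consent text says the same.

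The cost is one replaced sentence, two deleted words and one check of the consent text. No visit, test or procedure is added.

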#### **Other Exclusion Criteria**

- Prisoners or subjects who are involuntarily incarcerated.
- Subjects who are compulsorily detained for treatment of either a psychiatric or physical (e.g., infectious disease) illness.
- Patients who are active smokers
- Patients who are pregnant
- Nursing women
- Post-menopausal women who are on estrogen hormone replacement therapy will be excluded.
- Patients on low dose oral contraceptives will be allowed to participate as these formulations contain very low amounts of estrogens.

- Eligibility criteria for this study have been carefully considered to ensure the safety of the study subjects and to ensure that the results of the study can be used. It is imperative that subjects fully meet all eligibility criteria.

### **DISCONTINUATION OF SUBJECTS FROM TREATMENT**

Subjects **MUST** discontinue from the investigational product (and non-investigational product at the discretion of the investigator) for any of the following reasons:

- Withdrawal of informed consent (subject's decision to withdraw for any reason)
- Any clinical adverse event, laboratory abnormality, or inter-current illness which, in the opinion of the investigator, indicates that continued participation in the study is not in the best interest of the subject.
- Patients who progress to stages 3 and beyond, post screening will be excluded
- Pregnancy
  - Pregnant patients will be advised to contact the investigator or study staff immediately if they suspect they might be pregnant (e.g. missed or late menstrual period) at any time during study participation.
- Loss of ability to freely provide consent through imprisonment or involuntary incarceration for treatment of either a psychiatric or physical illness (e.g. infectious disease).
- If hyperglycemia and ketoacidosis is suspected, promptly discontinue treatment with Canagliflozin
- **All subjects who discontinue should comply with protocol-specified follow-up procedures outlined before.** The only exception to this requirement is when a subject withdraws consent for all study procedures or loses the ability to consent freely (i.e., is imprisoned or involuntarily incarcerated for the treatment of either a psychiatric or physical illness). If a subject withdraws before completing the study, the reason for withdrawal must be documented appropriately.

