--	---

Study Design:	Prospective, double-masked, randomized placebo-controlled trial
Accrual Goal (Total number of subjects):	N = 40
Accrual Rate (Number of subjects expected per month):	Recruit 40 patients in approximately 36 months
Estimated Timeline:	FPFV: 10-06-2016 LPLV: 01-06-2019
Co-relative studies (PK/PD, etc.):	N/A
Inclusion Criteria:	
 
1. Adults aged 30-70 years
 
2. Diagnosis of type 2 diabetes using criteria of the American Diabetes Association
 
3. Currently being treated with any combination of the following anti-diabetic therapies: metformin (1-2 grams), insulin, GLP-1 agonists, a DPP-IV inhibitor, or sulfonylureas as therapy for their Type 2 Diabetes
 
4. HbA1C between 7.0 to 10.0 % (both inclusive)
 
5. BMI 25 – 39.9 kg/m^2
 

Exclusion Criteria:	
Patients with:
 
 
1. Type 1 DM
 
2. History of hyperosmolar non-ketotic coma
 
3. Abnormal CBC that is judged by physician to be unsafe to enroll or low hematocrit (<28 UNITS).
 
4. History of Pancreatitis
 
5. History of DKA in the past 3 months
 
6. History of active cancer or cancer treatment in the past 5 years (except basal cell carcinoma)
 
7. Heart attack or stroke within 6 months of screening
 
8. Clinically significant coronary and/or peripheral vascular disease that would be unsafe to enroll in the study.
 
9. Statin use started or dose change in the last 3 months,
 
10. CKD stages 3B-5
 
11. Use of oral anti-diabetic medication other than metformin, insulin, GLP-1 agonists, DPP-IV inhibitors, or sulfonylureas
 
12. Use of consistent long-term steroid medication in the last 3 months (oral, inhaled, injected).
 
13. Uncontrolled inflammatory disease, or current chronic use of anti-inflammatory drugs within the last 3 months.
 
14. Pre-existing liver disease and/or ALT and AST >2.5X's UNL
 
15. Serum creatinine levels ≥2.0
 
16. Estimated CrCl < 45 mL/min (measured by eGFR value)
 
17. Triglycerides >450 mg/dL
 
18. Implanted devices (e.g., pacemakers) that may interact with Body Composition scale
 
19. Untreated Systolic Blood Pressure > 150 mmHg and diastolic Blood Pressure > 90 mmHg
 

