### **DOSE MODIFICATIONS**

No dose modification is necessary prior to CKD stage 3B (eGFR less than 45)

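### The renal stopping rule is set at CKD stage 3 (eGFR below 60), out of line with the limit of 45 used for entry and dosing, and cannot be applied clearly to patients who enter in stage 3A

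*Combined protocol and SAP*

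**What the plan says.** All references are to the combined protocol and SAP.

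- **Stopping.** Section 3, Discontinuation of Subjects from Treatment, lists reasons for which stopping the investigational product is mandatory. One is "Patients who progress to stages 3 and beyond, post screening will be excluded". A separate item covers "Any clinical adverse event, laboratory abnormality, or inter-current illness which, in the opinion of the investigator", judges that continuing is not in the subject's best interest. The section closes with "All subjects who discontinue should comply with protocol-specified follow-up procedures outlined before".
- **Staging.** The only staging scheme is the table in the Inclusion Criteria, which gives "3A Moderately decreased eGFR 45–59" and places 3B at 30-45.
- **Entry.** The Protocol Synopsis excludes "CKD stages 3B-5". The Exclusion Criteria in Section 3 exclude "CKD Stages 3B,4 and 5 (see definition above"), and Physical and Laboratory Test Findings exclude "Estimated CrCl < 45 mL/min (measured by eGFR value"). Serum creatinine of 2.0 or more is also excluded.
- **Dosing.** Section 4, Dose Modifications: "No dose modification is necessary prior to CKD stage 3B (eGFR less than 45").
- **Timing.** The Time and Events Schedule has biochemistry at screening and at weeks 0, 8 and 16, and dispenses drug at weeks 0 and 8.

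**The concern.** The stopping rule uses a renal limit 15 mL/min/1.73 m² higher than the limit for entry and dosing, and no section gives a reason. The gap is the whole of stage 3A, a group the plan admits and treats at full dose.

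Two difficulties follow for staff who must apply the rule patient by patient. First, two patients with the same eGFR are handled differently: one enrolled at 58 may continue, while one who falls from 62 to 58 must stop. Second, the rule has no clear meaning for a patient who enters in stage 3A. Either that patient already meets the condition, or cannot progress to a stage already reached, so that only a fall to 3B counts. Investigators could reasonably choose either reading.

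What is at stake is study treatment stopped without need, or stopped inconsistently, in a trial of 20 patients per arm.

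**Working it through.** The plan states no figure on this point, so there is none to reproduce. The check compares the limits and then converts them to serum creatinine (Scr).

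**1. The limits side by side**

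| Rule | Limit | eGFR 45-59 |
|---|---|---|
| Entry, by CKD stage | 3B or worse excluded | may enrol |
| Entry, by eGFR | below 45 excluded | may enrol |
| Dose change | below 45 | full dose |
| Mandatory stop | stage 3 or worse, so below 60 | stop, if reached by progression |

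The difference is 60 - 45 = 15 units.

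**2. Does the creatinine limit of 2.0 keep stage 3A out anyway?**

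The plan's CKD-EPI equation (Secondary Objective, serum biochemistry), inverted for Scr above κ, is

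Scr = κ × (A / eGFR)^(1/1.209), with A = 141 × 0.993^age (× 1.018 if female), without the race factor.

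Age 60 is used as an example:

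- Man: A = 92.5, κ = 0.9. eGFR 60 gives 0.9 × (92.5/60)^(1/1.209) = 1.29 mg/dL; eGFR 45 gives 1.63.
- Woman: A = 94.2, κ = 0.7. eGFR 60 gives 1.02 mg/dL; eGFR 45 gives 1.29.

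Over the eligible ages, Scr at eGFR 45 runs from 1.22 (woman aged 70) to 1.94 (man aged 30), always under 2.0. The race factor multiplies these values by 1.159^(1/1.209) = 1.130. For a man aged 30, eGFR 45 then lies at 1.94 × 1.130 = 2.19, above the limit, but eGFR 60 lies at 1.53 × 1.130 = 1.73, below it. Even there the upper part of stage 3A stays open. The creatinine criterion does not remove the gap.

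**3. How small a change triggers the rule?**

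A fall from 62 to 58 is a creatinine ratio of (62/58)^(1/1.209) = 1.057, a rise of 5.7%: 1.253 to 1.324 mg/dL in the 60-year-old man and 0.989 to 1.045 in the woman. The rule asks for no repeat reading. The same sensitivity exists at either limit: 62 to 60 is a 2.7% rise and 47 to 45 a 3.7% rise. These figures support a confirming test. They do not favour 45 over 60.

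**4. When can the rule act?**

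Treatment ends at week 16, so a week 16 value cannot shorten it. Of the scheduled on-treatment tests, only week 8 can, and it removes at most the second 8 of 16 weeks. Unscheduled tests are the other route.

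**The case against.** The best defence is that entry limits and on-treatment stopping limits do different jobs. A new decline to 58 can be a warning that a stable 58 is not, and any rule based on change will treat the two differently. A stricter limit may have been deliberate, and Dose Modifications concerns dose, not stopping. This stands as far as it goes: the plan is not self-contradictory, and a reader who infers a contradiction goes further than the text. It does not answer the stage 3A question, and nothing in the plan says that a margin was intended.

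Three other inferences are tempting and are not supported.

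- **That the rule catches patients at week 0, before any drug.** Week 0 does follow screening. But the section concerns stopping treatment, and a patient not yet treated has nothing to stop. The week 0 recheck in Study Design Overview names the inclusion criteria, whereas the renal limits are exclusion criteria, and the schedule marks the eligibility check only at the two screening steps.
- **That affected patients are dropped from the study and their data lost.** The word used for them is loose, but the opening of the list is about stopping the investigational product, and its last item asks those who stop to comply with follow-up.
- **That the follow-up sentence settles who is analysed.** It says nothing about analysis.

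It is also fair to object that moving to 45 relaxes a mandatory safety stop. A fall from 90 to 46 would no longer stop drug automatically. That cost is real.

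**Conclusion.** The concern holds as a minor point. The mandatory renal stop is out of line with the plan's other renal limits and cannot be applied clearly to patients who enter in stage 3A. The affected range is eGFR 45-59, about 1.29 to 1.63 mg/dL of creatinine in a 60-year-old man and 1.02 to 1.29 in a woman of that age. No effect on power, safety or the CD34+ outcomes is shown.

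The conclusion assumes that the stages in the stopping rule are those of the table in the Inclusion Criteria, the only staging in the document, and that stage 3 there means 3A and 3B together. The creatinine values assume no race factor.

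**What to change.** In Discontinuation of Subjects from Treatment, replace the renal item with wording such as: *Patients who progress to CKD stage 3B or beyond (eGFR below 45), confirmed on a repeat creatinine, will stop study drug and continue protocol-specified follow-up.*

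This matches the entry and dosing limits. It gives stage 3A entrants a clear rule. Stating the number also settles an eGFR of exactly 45, which the staging table places in both 3A and 3B. Steep declines that stay above 45 remain with the existing investigator-judgement item.

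The cost is one sentence in a protocol amendment and an occasional repeat creatinine; no visit is added to the schedule. The downside is the one named above: large falls that end above 45 rely on judgement and have no automatic stop.
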